## PROTOCOL AMENDMENT SUMMARY OF CHANGES TABLE

DOCUMENT HISTORY		
Document	Date	DNG Number
Amendment 5	12-MAY-2021	TMF-13331420
Amendment 4	17-FEB-2021	TMF-11820616
Amendment 3	24-JUL-2019	2017N332005_03
Amendment 2	24-SEP-2018	2017N332005_02
Amendment 1	20-FEB-2018	2017N332005_01
Original Protocol	09-FEB-2018	2017N332005_00

### Amendment 5: 12-MAY-2021

#### Overall Rationale for the Amendment:

Variability in the rate of change of  $\log_{10}$ CFU observed in the trial to-date is lower than anticipated. Due to this, and slower than anticipated recruitment, the study sample size has been re-calculated. The potential to modify the haemoglobin exclusion and stopping criteria in subsequent cohorts investigating lower doses of GSK3036656 has been added.

Further changes made to the protocol are detailed in the table below.

Section #	Description of Change	Brief Rationale
Section 1 Synopsis	
Changed from: "Up to 5 cohorts; 20 participants in each cohort (15 participants will receive GSK3036656, and 5 participants will receive SoC in each cohort)."
 
To: "Up to 5 cohorts; 12-20 participants in each cohort (9-15 participants will receive GSK3036656, and 3-5 participants will receive SoC in each cohort)."
	Updated to reflect changes in number of participants due to sample size re-calculations
Section 3.3.1 Risk Assessment	
Changed from: "Participants whose haemoglobin drops below pre-specified limits (<8.0 g/dL) will be withdrawn from the study (Section 8.1.3)."
 
To: "Participants whose haemoglobin drops below pre-specified limits will be withdrawn from the study (Section 8.1.3)."
	Removed specific value (<8.0 g/dL) as cross reference to Section 8.1.3 provides further information
Section 5.1 Overall Design	
Changed from: "The study will comprise up to 5 cohorts of participants. It is intended that 15 participants in each cohort will receive GSK3036656 and 5 will receive standard-of-care regimen for DS-TB (i.e. Rifafour e-275 or equivalent generic alternative)."
 
To: "The study will comprise up to 5 cohorts of participants. It is intended that 9-15 participants in each cohort (dependent on the cohort) will receive GSK3036656 and 3-5 will receive standard-of-care regimen for DS-TB (i.e. Rifafour e-275 or equivalent generic alternative), with a randomisation ratio of 3:1"
	Updated to reflect changes in number of participants due to sample size re-calculations
Section 5.1 Overall Design	
Changed from: "Cohorts will proceed sequentially starting A through D"
 
To: "Cohorts will proceed sequentially starting A through E"
	Corrected to align with study design of up to 5 cohorts

Section #	Description of Change	Brief Rationale
Section 5.1 Overall Design	
Changed from: "It is anticipated that it may be necessary to administer a dose of GSK3036656 the same or lower than in a previous cohort, dependent on preliminary safety, tolerability and pharmacokinetic data"
 
To: "It is anticipated that it may be necessary to administer a dose of GSK3036656 the same or lower than in a previous cohort, dependent on preliminary safety, tolerability, pharmacokinetic or efficacy data"
	Corrected to align with text in Section 11, Dose Escalation.
Section 5.3 Number of Participants	
Changed from: "Up to 20 participants will be enrolled into each cohort."
 
To: "It is intended that 12- 20 participants will be enrolled into each cohort, dependent on the cohort."
	Updated to reflect changes in number of participants due to sample size re-calculations
Section 5.3 Number of Participants	
Changed from: "If participants prematurely discontinue the study, additional replacement participants may be recruited at the discretion of the Sponsor in consultation with the Investigator."
 
To: "If participants prematurely discontinue the study, or if their respiratory sputum cultures are contaminated, additional replacement participants may be recruited at the discretion of the Sponsor in consultation with the Investigator."
	The primary endpoint for this study is derived from respiratory sputum cultures. If sputum cultures are contaminated, critical data for study analysis could be lost

Section #	Description of Change	Brief Rationale
Section 6.1 Inclusion Criteria	
Changed from: "6. Ability to produce an adequate volume of sputum as estimated from an overnight sputum collection sample (estimated 10 ml or more). (Estimated from a spot sputum sample and confirmed with the first overnight collection. If less than 10 ml is collected overnight this may be repeated once)."
 
To: "6. Ability to produce an adequate volume of sputum as estimated from an overnight sputum collection sample (estimated 10 mL or more). (If less than 10 mL is collected overnight this may be repeated once)."
	A random spot sputum sample does not provide a good estimation of a participant's ability to produce at least 10 mL sputum compared to a 16-hour overnight collection period, thus this sentence has been removed
Section 6.2 Exclusion Criteria	
Changed from: "13. Participants with the following abnormal laboratory values at screening as graded by the enhanced Common Terminology Criteria for Adverse Events (CTCAE v 5 2017):
 
a. haemoglobin <10.0 g/dL;"
 
To: "13. Participants with the following abnormal laboratory values at screening as graded by the enhanced Common Terminology Criteria for Adverse Events (CTCAE v 5 2017):
 
a. haemoglobin <10.0 g/dL; this criterion may be adjusted following DEC review (see Section 11)."
	Cross reference to Section 11 has been added and provides further details that the Dose Escalation Committee are empowered to make regarding haemoglobin exclusion criteria
Section 8.1.3 Haematology Stopping Criteria	
Changed from: "A reduction in haemoglobin to below 8.0 g/dL"
 
To: "A reduction in haemoglobin to below 8.0 g/dL; this criterion may be adjusted following DEC review (see Section 11)."
	Cross reference to Section 11 has been added and provides further details that the Dose Escalation Committee are empowered to make regarding haemoglobin stopping criteria

Section #	Description of Change	Brief Rationale
Section 9.1 Microbiological Efficacy/Activity Assessments	The following text was added: "MIC data reporting will likely occur after the clinical database has been authorised for the primary and secondary efficacy and safety endpoints at the end of the study (i.e. after Database Freeze [DBF]). The report detailing the data will remain as a separate report and will not be included in the GSK clinical study report."	The lab conducting microbiology assessments are in the process of validating the EUCAST liquid MIC protocol which will be used to determine the MIC. The lab will require additional time to validate the EUCAST MIC protocol, so the MIC data will be reported outside of the clinical study report
Section 9.4 Vital Signs	
Changed from:
 
"Vital signs (to be taken before blood collection for laboratory tests) will consist of at least 1 pulse and blood pressure measurement. Where a measurement is abnormal or significantly different from previous measurements, this will be repeated. Where BP and pulse is repeated above, a further 2 readings recorded at least 1 min apart will be obtained for confirmation and recorded in the CRF."
 
To:
 
"Vital signs (to be taken before blood collection for laboratory tests) will consist of at least 1 pulse and blood pressure measurement. Where a measurement is abnormal or significantly different from previous measurements, a further 2 readings will be taken. When vital signs are measured in triplicate, values should be taken at least 1 minute but not more than 5 minutes apart and recorded in the CRF."
	Updated to specify window for repeat vital signs, as documented in the Study Reference Manual
Section 10.1 Sample Size Determination	Details of Sample Size Re-estimation added (Section 10.1.2) and separated from Original Sample Size Calculations (Section 10.1.1)	Variability in the rate of change of log 10 CFU observed in the trial to-date is lower than anticipated. Due to this, and slower than anticipated recruitment, the study sample size has been re-calculated.

Section #	Description of Change	Brief Rationale
Section 10.3.1 Activity/ Pharmacokinetic Analyses	For the analysis of the primary endpoint, EBA CFU 0-14 , and the secondary endpoints, EBA CFU 0-2 , EBA CFU 2-14 , EBA TTP 0-14 , EBA TTP 0-2 and EBA TTP 2-14 , the covariates to be included in the mixed model have been changed from dose and baseline value, to treatment, day, BMI and treatment-by-day	A repeated measures analysis, including day as a covariate is more appropriate for measuring the rate of change over the treatment period. Dose has been replaced by treatment, with data for participants receiving standard-of-care included, and BMI has been added due to its potential influence on the EBA endpoints.
Section 11 Dose Escalation	
Changed from: "PK data in at least 10 subjects receiving GSK3036656 and selected safety data from all subjects in a cohort."
 
To: "PK data in at least 7 subjects receiving GSK3036656 and selected safety data from all subjects in a cohort"
	Based on the PK variability observed in the first two Cohorts, a sample size of 7 will give at least 80% power in the derivation of key PK parameters with an acceptable precision.
Section 11 Dose Escalation	
Changed from: "The primary endpoint may be analysed for all available cohorts after the final visit of the last subject on the second consecutive cohort that reaches or exceeds the target PK plasma exposure for efficacy (based on the murine infection model), and subsequent cohorts."
 
To: "The primary endpoint may be analysed once data is available for 12 evaluable subjects, as per the sample size re-estimation calculations, on the second consecutive cohort that reaches or exceeds the target PK plasma exposure for efficacy (based on the murine infection model), and subsequent cohorts."
	Updated to reflect changes in number of participants due to sample size re-calculations

Section #	Description of Change	Brief Rationale
Section 11 Dose Escalation	The following text was added: "To adjust the haemoglobin exclusion and stopping criteria if no haematological abnormalities are observed in the review of safety data from the highest dose cohort (Cohort 3). For the subsequent cohort(s) receiving a lower dose of GSK3036656, the haemoglobin exclusion criterion will be lowered to <8.0g/dL, and the haemoglobin stopping criterion will be lowered to <6.0g/dL. Patients with a confirmed haemoglobin <8.0g/dL after randomisation will require enhanced observations, with a repeat haemoglobin level and discussion of patient status with the GSK medical monitor."	A high number of screen fails have occurred due to haemoglobin levels being slightly lower than the current exclusion criteria (<10.0 g/dL), which is a common characteristic in this study population.

## 1. SYNOPSIS

**Protocol Title:** A Phase IIa open-label trial to investigate the early bactericidal activity, safety and tolerability of GSK3036656 in participants with drug-sensitive pulmonary tuberculosis.

**Short Title:** GSK3036656 EBA Study

### Objectives and Endpoints:

Objectives	Endpoints

Primary
 
 
To determine the early bactericidal activity of GSK3036656 over 14 days of once daily repeat dosing.
 
	
 
Rate of change in log10CFU per mL direct respiratory sputum samples over the period baseline to Day 14 (EBA CFU0-14).
 

Secondary
 
 
To assess the safety and tolerability of GSK3036656 administered once daily over 14 days to participants with tuberculosis.
 
To characterise the pharmacokinetics of 14-day once daily dosing of GSK3036656 in tuberculosis participants.
 
To determine the early bactericidal activity of GSK3036656 over the first 2 days and the last 12 days with 14 days of once daily repeat dosing.
 
	
 
Adverse events (AE), clinical laboratory values, vital signs, electrocardiogram (ECG) parameters.
 
Derived pharmacokinetic parameters for GSK3036656 including area under the plasma drug concentration versus time curve (AUC0-t, AUC0-24), maximum observed plasma drug concentration (Cmax), and time to maximum observed plasma drug concentration (tmax), as appropriate.
 
Rate of change in log10CFU per mL direct respiratory sputum samples over the period baseline to Day 2 (EBA CFU0-2).
 
Rate of change in log10CFU per mL direct respiratory sputum samples over the period Day 2 to Day 14 (EBA CFU2-14).
 
Rate of change in time to sputum culture positivity (TTP) over the time period baseline to Day 14 (EBA TTP0-14).
 

Objectives	Endpoints
	
 
• Rate of change in time to sputum culture positivity over the time period baseline to Day 2 (EBA TTP0-2).
 
• Rate of change in time to sputum culture positivity over the time period Day 2 to Day 14 (EBA TTP2-14).
 

Exploratory  
CCI
	

For the purpose of assessment of bacterial CCI endpoints, the pre-treatment baseline will be defined as the mean of Day -2 and Day -1; if data is available at only Day -2 or Day -1 then that value will be used as baseline. For ECG endpoints, baseline is screening CCI

### Overall Design:

A single-centre, open-labelled, clinical trial in up to five sequential cohorts of participants with rifampicin-susceptible tuberculosis (DS-TB). Each cohort will involve participants being randomised to one of two possible treatments: either GSK3036656 or Standard-of-care (SoC) regimen for DS-TB (i.e. Rifafour e-275 or equivalent generic alternative). The ratio of participants assigned to GSK3036656 vs Rifafour e-275 (or equivalent generic alternative) will be 3:1.

The starting dose is set at 5 mg once daily (with a 15mg loading dose on day 1) given orally and the study will employ dose escalation, where the dose for each cohort will be decided based on reviews of preliminary safety, tolerability and pharmacokinetic data. This includes the possibility of subsequent doses being less than or the same as a preceding dose, if appropriate.

After the initial dose of GSK3036656, the decision to proceed to each subsequent dose level will be made by the Dose Escalation Committee (DEC) based on safety, tolerability and preliminary pharmacokinetic data from the prior cohort. The DEC may also include efficacy data in their deliberations, if that is available.

**Number of Participants:** up to approximately 100 participants will be enrolled.

**Treatment Groups and Duration:** Up to 5 cohorts; 12-20 participants in each cohort (9-15 participants will receive GSK3036656, and 3-5 participants will receive SoC in each cohort).

The approximate duration of the study for an individual participant is anticipated to be 5 weeks to include a maximum of 1 week for screening, 2 days of baseline sputum sample collection, 2 weeks for the treatment period and another 2 weeks for the final follow-up visit.

## 2. SCHEDULE OF ACTIVITIES (SOA)

Period	Screening			Dosing						Follow-up	
Visit	1	2	3	4	5 to 10	11	12 to 16	17	18	Early Withdrawal	19
Day	(-9 to -3) A	-2 B	-1	1	2 to 7 C	8	9 to 13 C	14	15		28 (± 7)
Documentation of Positive GeneXpert and/or TB smear (TB clinic/site of initial diagnosis)	X										
Written Informed Consent	X										
Demography (including smoking history)	X										
Medical & Treatment History	X										
Inclusion/Exclusion/Eligibility Assessment	X										
Chest X-ray	X										
Physical Examination D	X			X	X	X	X	X	X	X	X
Vital Signs E	X	X	X	X	X	X	X	X	X	X	X
12-Lead ECG	X								X	X	X
Randomisation M		X									
Echocardiogram (may be conducted at any of the screening visits)	X									X S	X S
Blood PK F							X F	X	X	X	
Spot Sputum (confirm TB & adequate bacterial load) G	X										
Rifampicin Resistance Test (rapid) G (microscopy and GeneXpert tests may be repeated on an overnight sputum sample if needed)	X										
Haematology, Clinical Chemistry, Urinalysis H	X			X	X	X		X		X	X
Cardiac safety biomarkers T	X			X	X			X			
Urine Drug Screen I	X	X I									

Period	Screening			Dosing						Follow-up	
	1	2	3	4	5 to 10	11	12 to 16	17	18	Early Withdrawal	19
Visit											
Day	(-9 to -3) A	-2 B	-1	1	2 to 7 C	8	9 to 13 C	14	15		28 (± 7)
HIV Test (and CD4 Count if HIV confirmed)	X										
CCI				X	X			X		X	
				X	X			X		X	
			X					X			
Hospital Admission	X B	X B									
Overnight Sputum L	X	X	X	X	X	X	X	X			
IP Administration and Compliance Check N				X	X	X	X	X			
Mycobacteriology Assessments O		X	X					X			
Hospital Discharge									X	X	
Concomitant Medication		X	X	X	X	X	X	X	X	X	X
Adverse Events P				X	X	X	X	X	X	X	X
Point of Care Blood Glucose or HbA1c Q			X					X			

- A. The Visit 1 (day -9 to -3) time period will be up to a maximum of 7 days but will be kept as short as possible.
- B. Participants can proceed with the Visit 2 (day -2) assessments as soon as their Visit 1 (day -9 to -3) assessments have been completed i.e. Visits 1 and 2 may occur on the same day as long as the screening results are available in time for randomisation. Participants may be hospitalised during the entire pre-treatment period if the Investigator considers it advisable for reasons of safety or compliance.
- C. All events listed as occurring on Visit 5 (day 2) to Visit 10 (day 7) and Visit 12 (day 9) to Visit 16 (day 13) will be conducted each day during these visits.
- D. Height (m) will only be collected once at Visit 1 (day -9 to -3). A full physical examination will be performed at Visit 1 (day -9 to -3), with symptom-directed physical examinations at Visit 17 (day 14), Visit 19 (day 28) and Early Withdrawal Visit (EWV). Symptom directed physical examinations may be conducted as required during the study (visits 4 to 16). Requirements for the physical examination are specified in the SRM.
- E. Systolic blood pressure (SBP) and diastolic blood pressure (DBP) (mmHg), heart rate (beats per minute [bpm]), body temperature (°C), respiratory rate (breathes per minute) and weight (kg). To be performed within 4 hours prior to the first daily dosing on Visit 4 (day 1) through to Visit 17 (day 14) and within 4 hours before the time dosing would have occurred on Visit 18 (day 15). On days where the following assessments are done the order should be: vital signs before blood draws for PK or safety assessments.
- F. PKs will be performed as noted in the PK table. A single pre-dose PK sample will be collected on each of Days 12 & 13, and serial PK blood sampling will occur on Day 14 (see PK table below). At EWV a PK sample will be taken before the time of the planned daily dosing. If this is not possible, a spontaneous PK sample will be taken.

- G. Sputum smear microscopy and molecular rapid test for confirmation of Mycobacterium tuberculosis and rifampicin susceptibility (GeneXpert). If the first spot sputum or overnight sputum sample shows an unfavourable result, the tests may be repeated on a freshly collected spot sputum or overnight sputum sample and that result used instead.
- H. ). Refer to [Appendix 3](#) for details.
- I. Urine drug screen: cocaine, amphetamines and opiates. Urine drug screen can be repeated at Visit 2 (day -2) for participants who were not hospitalized at Visit 1 (day -9 to -3).
- J. CCI
- K. [REDACTED]
- L. Overnight sputum sampling may start at Screening visit (day -9 to -3) or on Visit 2 (day -2) and will continue daily until Visit 7 (day 4). Additional sampling will be conducted at visit 9 (day 6), Visit 11 (day 8), Visit 13 (day 10), Visit 15 (day 12) and Visit 17 (day 14). Sputum sampling will stop on the morning of Visit 18 (day 15). Sputum collection will start in the afternoons at 15:00 hours ( $\pm 1$  hour) and continue for 16 hours overnight. The 16-hour sputum sampling for each of the sampling days must be finished prior to the administration of the next day's IP.  
Overnight sputum collection may be collected as many times as required over the screening period until an eligible sample is obtained. Of the pre-treatment period samples collected, only the Visit 2 (day-2) and Visit 3(day -1) overnight sputum samples will be used for the efficacy endpoint tests.  
The day sputum collection starts reflects the day to which that sample applies. e.g. a sample whose collection starts on day 1 and ends on day 2, is designated as the day 1 overnight sputum sample (and results).
- M. Randomization may occur once all the screening results are available and the Investigator has determined that the participant is eligible for the trial.
- N. After the first dose of IP, subsequent doses of IP will be administered 23 to 25 hours after the previous dose.
- O. Minimum inhibitory concentration (MIC) and speciation of the infecting organism by polymerase chain reaction (PCR) will be estimated from a culture collected on a pre-treatment day (day-1 or day-2) and from the last available culture on a treatment day (day 14 or earlier, but not earlier than day 8). Drug susceptibility testing of *M. tuberculosis* for sensitivity to rifampicin with a molecular method will be tested at Visit 1. Susceptibility to INH, Rif, EMB and PZA will be tested on a culture grown from a baseline sample (day -2 or day -1). The analysis of any bacterial isolates sent to GSK, Spain for further characterisation in the event of MIC change will not be reported in the clinical study report and will be reported separately.
- P. Adverse events (AE) will be collected by the Investigator from the time a participant receives his/her first dose of IP through to the Visit 19 (day 28) Follow up Visit.
- Q. CCI
- R. [not used]
- S. Only to be performed on participants as determined by the dose escalation committee (DEC) or on participants with changes in clinical status warranting a follow-up echo in the opinion of the investigator. The DEC may decide to perform this assessment in additional cohorts within this study.
- T. Samples will be assayed for: Troponin I. The first two samples at least 24 hours apart, one during the screening phase and one prior to the first dose of study treatment. Day 14 sample window is  $\pm 24$  hours. Third sample to be taken on Day 3.

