**PK sampling time and events table**

STUDY VISIT	Visit 15	Visit 16	Visit 17										Visit 18
STUDY DAY	Day 12	Day 13	Day 14										Day 15
STUDY HOUR B			0	0.5	1	1.5	2	3	4	6	8	12	24
Pharmacokinetic sampling C	X A	X A	X D	X	X	X	X	X	X	X	X	X	X

- A. Sample to be taken within 30 minutes pre-dose.
- B. All values are relative to the time of day that the study treatment is administered on Day 14.
- C. PK sampling is only to be performed on participants receiving GSK3036656. PK samples will not be taken from participants receiving Rifafour e-275 (or equivalent generic alternative).
- D. Sample to be taken within 10 minutes pre-dose

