## 5.6. Dose Justification

A population pharmacokinetic model was developed based on preliminary concentration-time data obtained in the FTIH study. The model was used to simulate loading and maintenance doses for GSK3036656 based on the EBA study design and accounting for

the effect of renal impairment on exposure (preliminary data suggest GSK303656 is > 70% renally excreted). A target exposure for efficacy of 1.74 ug.h/mL was set based on the exposure associated with efficacy in a mouse infection model and the target attainment rate was defined as the percentage of participants with an AUC0-24 greater than this target exposure. Exposure limits of AUC0-24 of 15 ug.h/mL and Cmax of 1.5 ug/mL were set, based on information in Section 3.3.

A loading dose of GSK3036656 may be administered on the first day (or over multiple days where required in order to not exceed AUC and Cmax exposure limits) of study treatment administration in each cohort. The long half-life of GSK3036656 (45 hours) means that subjects will take up to 10 days to reach steady-state concentrations, which is not optimal for a 14-day treatment study. A loading dose will allow participants to reach steady-state concentrations in 2 to 3 days for a given maintenance dose regimen.

The probability rates for individual participants to exceed GSK3036656 exposure limits and achieve the efficacy target for proposed loading and maintenance dose regimens are shown in Table 1.

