**Table 1 Probability rates of individual participants for proposed loading and maintenance doses**

Loading Dose (mg) a	Probability Day 1 c	Maintenance Dose (mg) b	probability Day 14 d	Target Attainment Rate e
15	<1%	5	<1%	<1%
25	<1%	10	<1%	100%
50	<1%	20	<1%	100%
75	6.90%	30	5.80%	100%
a Day 1				
b Day 2-14				
c per trial probability of an individual participant exceeding the exposure limits [AUC 0-24 = 15 ug.h/mL or C max = 1.5 ug/mL] on Day 1 (simulations based on a lower limit of 75 mL/min for creatinine clearance)				
d per trial probability of an individual participant exceeding the exposure limits [AUC 0-24 = 15 ug.h/mL or C max = 1.5 ug/mL] on Day 14 (simulations based on a lower limit of 75 mL/min for creatinine clearance)				
e per trial probability of >90% of participants exceeding the target exposure for efficacy				

The starting dose regimen for this study will be 15 mg loading dose on Day 1 and 5 mg maintenance dose on Day 2-14, based on the above information, with the option to

investigate a lower dose in subsequent cohorts should the preliminary data indicate this is appropriate.

The loading dose (if applicable) and maintenance dose for each cohort will be chosen on the basis that it is not predicted to exceed the pre-specified safety cap, and the dose used will be decided by the Dose Escalation Committee (Section 11).

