## 8.2. Individual/Cohort Stopping Criteria

For an individual study participant, stopping criteria include, but are not limited to:

- Severe signs or symptoms, or significant changes in any of the safety assessments that put the safety of the individual at risk (e.g. ECG, vital signs, laboratory tests etc.), as judged by the Investigator, in consultation with the Medical Monitor if necessary.
- Any unacceptable adverse event that is thought to be related to the investigational product and any general safety finding that, in the opinion of the Investigator, gives cause for concern may result in the withdrawal of subject(s) and/or the study being paused or terminated and/or a dose adjustment.

Dose escalation will be stopped if any of the following occurs in a cohort:

1. There is substantially increased incidence and/or severity of clinically significant adverse events or withdrawals possibly related to GSK3036656 in the GSK3036656 treatment subgroup at the last dose level administered as compared to the SoC subgroup. The Dose Escalation Committee in conjunction with the study Investigator will determine the significance of the adverse events or withdrawals and make a decision about whether stopping further dose escalation is necessary.
2. At least one subject has a plasma AUC0-24 or Cmax higher than the exposure limits set in Section 5.6.

If dose escalation is stopped due to reasons 1 or 2 above occurring at the last dose, dosing at a lower level could be allowed by the Dose Escalation Committee. The Dose

Escalation Committee will decide whether dosing at such level could be done and will select the dose to be administered.

Further details regarding dose escalation and the Dose Escalation Committee composition and remit are in Section 11.

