## 11. DOSE ESCALATION

After the initial dose of GSK3036656, the decision to proceed to each subsequent dose level will be made by the Dose Escalation Committee (DEC) based on safety, tolerability and preliminary GSK3036656 pharmacokinetic data from the prior cohort. The DEC may also include in their deliberations, efficacy data, if that is available. Minimum requirements for data are as follows: PK data in at least 7 subjects receiving GSK3036656 and selected safety data from all subjects in a cohort. A dose escalation committee charter will be produced that will contain the following details:

- Committee members
- Data review requirements
- Process for informing the ethics committee of any safety concerns if appropriate
- Facility for requesting additional pertinent information from the investigator

Dose escalation will be based on population PK modelling (if feasible). Dose escalations will not be higher than 3-fold.

The population PK model will be a fit for purpose model. Candidate model selection will be primarily based on a significant reduction in the objective function value ( $\geq 3.32$ ,  $\chi^2 < 0.05$ ) and improvement in the fits of diagnostic scatter plots. Inter-individual variability will be modelled using an exponential error model and residual error will be described by a proportional, proportional plus additive, or additive error model, depending on the data. Model performance will be evaluated using a visual predictive check. Simulations for dose recommendations will be conducted to determine the probability of an individual subject exceeding the defined exposure margins for AUC and Cmax.

Alternatively, if a population PK model is not feasible, dose escalation will be based on a dose-exposure model of the form:

$$\log(\text{AUC}) = a + b \cdot \log(\text{DOSE}) + c \cdot \log(\text{BWT}/70)$$

$$\log(\text{C}_{\text{MAX}}) = d + e \cdot \log(\text{DOSE}) + f \cdot \log(\text{BWT}/70)$$

where a and d are AUC and Cmax values, respectively; c = -0.75 and f = -1.00 are set values for allometric scaling; and b and e are scaling factors for dose proportionality.

A proposed dose will be acceptable if the predicted probability of an individual exceeding pre-defined exposure limits (Section 5.6) on any day of the dosing period, as estimated by PK modeling, is no more than 10%.

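### Scheduled PK samples give no observed Day 1 exposure, so the rule that stops escalation on the exposure limits cannot detect a loading-dose exceedance from them

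*Protocol*

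**What the plan says.** **Sampling.** Protocol Section 2, footnote F: "A single pre-dose PK sample will be collected on each of Days 12 & 13, and serial PK blood sampling will occur on Day 14". The PK sampling table has columns for Days 12, 13, 14 and 15 only, and its footnote B reads "All values are relative to the time of day that the study treatment is administered on Day 14". SAP Appendix 2 repeats the schedule. Other samples are incidental. Footnote F adds "At EWV a PK sample will be taken before the time of the planned daily dosing"; Section 9.3 allows one after an overdose, and Appendix 7 asks for one after a liver event on GSK3036656. None is designed to give a Day 1 profile.

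**Limits and loading dose.** Section 5.6: "Exposure limits of AUC 0-24 of 15 ug.h/mL and C max of 1.5 ug/mL were set". The same section allows a loading dose on Day 1, or spread over several days to respect the limits. Table 1 gives Day 1 and Day 14 separately, each defined as the "per trial probability of an individual participant exceeding the exposure limits".

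**Stopping escalation.** Section 8.2, item 2: "At least one subject has a plasma AUC 0-24 or C max higher than the exposure limits set in Section 5.6". It names no day and does not say whether the value must be observed or may be model-derived.

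**Choosing a dose.** Section 11 accepts a dose if the predicted probability that an individual exceeds the limits "on any day of the dosing period, as estimated by PK modeling, is no more than 10"%.

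**The concern.** Section 3.3.1 says the heart valve and vascular pathology cannot be monitored in humans, so the exposure limits are the main protection. Section 5.5 says PK in TB participants was unknown at design. Section 8.2 item 2 is the rule that responds to the exposures participants actually had; the Section 11 criterion works beforehand, on predictions. In Table 1 the Day 1 dose is 2.5 to 3 times the maintenance dose, yet no exposure is measured on that day.

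What is at stake is what the DEC and the report can claim. A cohort could be described as within limits when one of the two days simulated in Table 1 was never observed. The planned displays would not reveal this: SAP Figures 4.2 to 4.4 use Day 14 and 15 data, and the dose-proportionality shell (PK_T1) lists Day 14 only.

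**Working it through.** **1. Can the Table 1 figures be reproduced?** No. They come from population PK simulation, and the documents give no clearance, volume, absorption or variability parameters. They can only be read:

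| Loading / maintenance (mg) | Day 1 | Day 14 |
|---|---|---|
| 15 / 5 | <1% | <1% |
| 25 / 10 | <1% | <1% |
| 50 / 20 | <1% | <1% |
| 75 / 30 | 6.90% | 5.80% |

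**2. Do the late samples carry information on Day 1?** With the 45 h half-life in Section 5.6, the fraction of the Day 1 dose remaining at time t is exp(−ln 2 × t/45).

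- Day 12 pre-dose (264 h, 5.9 half-lives): 1.7%
- Day 13 pre-dose (288 h): 1.2%
- Day 14 pre-dose (312 h, 6.9 half-lives): 0.8%
- 24 h after the Day 14 dose (336 h): 0.6%

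There is almost no direct information. A population PK model fitted to the Day 14 profiles can still predict an individual's Day 1 exposure, but that estimate rests on the model. The Section 11 fallback, a regression of log AUC or log Cmax on log dose and weight, has no time term. Fitted to this trial's data, it cannot separate Day 1 from Day 14.

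**3. What share of exceedances would Day 14 miss at 75/30 mg?** Let a = 6.9% (Day 1) and b = 5.8% (Day 14), read as per-trial probabilities. The missed share is 1 − b / P(either day).

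| Assumption | P(either day) | Missed share |
|---|---|---|
| Nested: Day 14 exceedances all occur on Day 1 too | 6.9% | 1 − 5.8/6.9 = 16% |
| Bivariate normal, correlation 0.95 | 8.0% | 27% |
| Bivariate normal, correlation 0.8 | 9.4% | 39% |
| Independent | 1 − 0.931 × 0.942 = 12.3% | 53% |
| Disjoint | 6.9% + 5.8% = 12.7% | 54% |

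The correlations are assumptions. The last two rows are implausible, because the same participant's renal clearance drives exposure on both days.

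**4. If Table 1 is per individual.** The footnote wording allows this reading. With independent participants, P(at least one) = 1 − (1 − p)^n.

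| Participants with PK data | Day 1 | Day 14 | Missed share, nested |
|---|---|---|---|
| 7 (DEC minimum) | 39.4% | 34.2% | 1 − 34.2/39.4 = 13% |
| 9 | 47.5% | 41.6% | 1 − 41.6/47.5 = 12% |
| 15 | 65.8% | 59.2% | 1 − 59.2/65.8 = 10% |

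The missed share of cohorts is a little lower, but exceedances would be far more common.

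**5. Is Day 1 really the riskier day?** The gap is 1.1 percentage points. Treating the two days as independent, it is about 1.0 standard error with 1,000 simulated trials and 3.2 with 10,000; the number run is not given. A one-compartment check at a 45 h half-life (daily retention r = exp(−ln 2 × 24/45) = 0.691) gives an amount after the Day 14 dose of 75r¹³ + 30(1 − r¹³)/(1 − r) = 96.9 mg. Day 1 is then 75/96.9 = 77% of Day 14. The Table 1 ordering must come from model features the documents do not show. The point does not depend on the ordering, only on Day 1 being unobserved.

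All figures use the protocol's limits. SAP Section 3.1 still carries 4.9 µg·h/mL and 0.443 µg/mL, a separate inconsistency.

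**The case against.** Day 1 is not ignored. The Section 11 criterion covers every dosing day, and 6.90% passes it. Section 5.6 requires that neither the loading nor the maintenance dose is predicted to exceed the cap. The DEC may add PK assessments, and Section 9 lets assessment times change without an amendment. Section 8.2 item 2 does not demand observed values, so model-derived Day 1 estimates might already count; the DEC charter or the population PK analysis plan, neither of which is in these documents, may say so. Section 11 calls Cohort 3 the highest-dose cohort and refers to lower doses afterwards, and SAP Section 5.1 lists 30 mg as Dose 3, so a missed halt to escalation may matter little in practice. The cap sits 10-fold below the lowest NOAEL in the 17-week studies, and troponin is taken on Day 3.

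Much of this stands, and it limits the weight of the point. It does not close the gap. The added sampling is optional and names no day, and nothing in the two documents links Section 8.2 or the reported PK to Day 1 exposure. Section 11 still allows a higher dose, and SAP Doses 4 and 5 are open. The safety margin and troponin do not show whether the limits were kept.

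A reader might infer more: that the rule is blind to Day 1 altogether, that half of exceedances would be missed, or that Day 1 is clearly the worse day. The documents do not support these. The rule's wording leaves room for model estimates, the 53–54% figures need independent or disjoint days, and the ordering rests on a small gap at one regimen. Nor do they say that 75 mg was the load given with 30 mg.

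**Conclusion.** The point holds as a mismatch between the scope of a rule and the data scheduled to feed it. The planned samples yield no observed Day 1 AUC0-24 or Cmax. Section 8.2 item 2, applied to them, cannot detect a loading-dose exceedance, and Day 1 is covered only by prediction at dose selection.

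The size is modest and confined to the top Table 1 regimen. The missed share is at least about 16% of trials with an exceedance, if Table 1 is per trial; that is the nested case, and higher shares need weaker within-person correlation. If Table 1 is per individual, the nested share of cohorts is 10% to 13%. Both use the 75/30 mg figures as printed. At the other three regimens Table 1 gives less than 1% on both days.

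The documents give no evidence that anyone exceeded a limit on Day 1. They also provide no observed data that could show nobody did.

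**What to change.** - Reconcile Protocol Section 8.2 item 2, Section 11 and the PK schedule in Section 2, so that they state together which day(s) the exposure limits are checked on and against which estimates, observed or model-derived.
- As an added analysis output, report each GSK3036656 participant's estimated Day 1 AUC0-24 and Cmax from the population PK model already planned for escalation. Give these to the DEC and put them in the report, labelled as model-derived.
- If this is not done, or the population model proves infeasible, state in the report that the limits were verified on observed data on Day 14 only.

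The cost is one extra output from a planned model and some wording. The drawback is that the Day 1 estimates lean on the model, since about 1% of the Day 1 dose remains by Day 14. No dose, limit or stopping rule is proposed here.
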